3.1.1. Screening Phase

Subjects will be recruited from the Medical Oncology, Radiation Oncology, and Neurosurgery practices at the University of Pennsylvania Health System. The treating physician will determine

if the patient is a potential research candidate. The treating physician will approach and inform the patient about the study, thereby initiating the informed consent process. If the patient expresses interest in the study, the treating physician will contact a qualified member of the research team in the Neurosurgery Clinical Research Division at the University of Pennsylvania and request availability for enrollment. A sub-investigator will continue the formal consent process. This person will explain the requirements of the study and provide a copy of the Informed Consent Form. The person obtaining consent will state the volunteer nature of research and advise the subject to take sufficient time to discuss the study before making her decision to sign the informed consent document. If a decision to participate is made, the informed consent form is signed after which screening procedures will be performed. Subject eligibility will be evaluated based upon the criteria outlined in the protocol. After eligibility is established, a subject study number will be issued. Eligibility is confirmed with a clinically-licensed study Investigator. All members of the research team will have successfully completed patient oriented research training.

3.1.2. Study Intervention Phase

Schema (Figure 5):

Cohort A (non-surgical; N=16):

Within 7 days of enrollment, the subject will receive a single 500mg dose of INCMGA00012 and a single 300mg dose of INCAGN01876 on the same day. Within 3 to 7 days following these

doses, the subject will receive stereotactic radiosurgery (SRS), administered over the course of 3 consecutive business days (8 Gy x 3 fractions, one fraction per day, total dose 24 Gy). Subjects may receive 3 fractions every other day (non-consecutively) for logistical reasons relating to COVID-19. Following SRS, the two study drugs will be resumed according to their respective dosing schedule (INCMGA00012 500 mg IV every 4 weeks; INCAGN01876 300mg IV every 2 weeks). For example, INCAGN01876 will be resumed 2 weeks from the date that the first pre-SRS dose was given, and INCMGA00012 will be resumed 4 weeks from the date that the first pre-SRS dose was given. Subjects will continue on combined systemic treatment (INCMGA00012 500 mg IV every 4 weeks and INCAGN01876 300mg IV every 2 weeks) until disease progression, unacceptable AEs, or for 2 years, whichever occurs first.

Cohort B (surgical; N=16):

Subjects in cohort B are enrolled onto one of two surgical sub-arms (sub-arms 1 or 2; eight subjects per sub-arm), with each sub-arm receiving a different neoadjuvant regimen prior to surgical resection as diagrammed above in the study schema. The two possible neoadjuvant regimens are INCMGA00012 + INCAGN01876, or INCMAG00012 + INCAGN01876 + SRS. Subjects with a tumor that is amenable to SRS (i.e., as determined by the Investigator) are assigned to sub-arm 1 (INCMAG00012 + INCAGN01876 + SRS) until this arm has reached its total enrollment (N=8). All other subjects enrolled in Cohort B are assigned to the other surgical sub-arm (sub-arms 2; INCMGA00012 + INCAGN01876, without SRS).

In both surgical sub-arms, within 7 days of enrollment the subject will receive a single dose of the investigational systemic agent(s) according to the sub-arm to which he/she is assigned. In sub-arm # 1 (INCMAG00012 + INCAGN01876 + SRS), within 3 to 7 days following the neoadjuvant doses of the systemic study drugs, the subject will receive SRS, administered over the course of 3 consecutive business days (8 Gy x 3 fractions, one fraction per day, total dose 24 Gy). Subjects may receive 3 fractions every other day (non-consecutively) for logistical reasons relating to COVID-19. Within 7-14 days following administration of the study drug(s) (surgical sub-arms # 2) or within 7-14 days following SRS (surgical sub-arm # 1), the subject will undergo maximal safe surgical resection of the tumor. Following surgery, the subject will then resume systemic therapy with BOTH investigational agents INCMGA00012 and INCAGN01876 (regardless of which of the two sub-arms the subject was assigned to). The systemic agents should be started as soon as the investigator feels the subject has recovered adequately from surgery, but must be restarted within 5 weeks (35 days) from the date of surgery. Subjects will continue on combined systemic treatment (INCMGA00012 500 mg IV every 4 weeks and INCAGN01876 300mg IV every 2 weeks) until disease progression, unacceptable AEs, or for 2 years, whichever occurs first.

3.1.3. Follow Up Phase

Any subject who permanently discontinues the study drugs based on any reason outlined in [Section 5.7](#) will proceed to follow-up.

3.1.3.1. Safety Follow-Up

A scheduled safety follow-up visit occurs 30 (+/- 7) days after the EOT visit (the visit that occurs when subjects are taken off study treatment (see [Section 6](#); [Table 8](#) and [Table 9](#) for full schedule of events). Reasonable efforts should be made to have the subject return for the follow-up visit and report any AEs that may occur during this period. If the subject cannot return to the site for

the safety follow-up visit, the subject is contacted by telephone for collection of AEs and SAEs, and this should be documented in the eCRF.

Following the scheduled 30-day safety follow-up visit, subjects are contacted by telephone, e-mail or visit one additional time 12 weeks (+/- 14 days) from the EOT visit to capture additional immune related AEs (see sections 1.3.1.3 and 1.3.2.3).

3.1.3.2. Disease Status Follow-Up

Subjects who discontinue study drug treatment but who have not yet met criteria for disease progression are assessed by radiologic imaging to monitor disease status. These assessments occur every 12 weeks (\pm 14 days). The imaging assessments occur at the study site if the subject continues to receive care at the University of Pennsylvania; otherwise, research staff will obtain subject's outside radiology reports and outside physician notes to determine disease status. If possible, the original images from radiology scans will also be obtained for formal radiologic interpretation by University of Pennsylvania Neuroradiology.

Every effort should be made to collect information regarding disease status until:

- The start of new antineoplastic therapy.
- Disease progression.
- Death.
- Termination of the study
- 5 years after removal from protocol therapy

3.1.3.3. Survival Follow-Up

Subjects are contacted by telephone, e-mail, or visit every 12 weeks (+/-14 days) from the 12-week safety follow-up visit to capture survival status until death, withdrawal of consent, termination of the study or 5 years after removal from protocol therapy, whichever occurs first. Public records/databases are searched if contact with the subject is lost.

For participants who are thought to be lost to follow-up, at least 3 documented attempts should be made to contact the participant before the participant is deemed lost to follow-up.

3.2 Replacement of Subjects

Cohort A: Any subject who is enrolled onto Cohort A of the study but meets one of the following criteria is replaced by enrollment of a new subject onto Cohort A:

- The subject is enrolled, but does not receive BOTH systemic agents (INCMGA00012, INCAGN01876)
- The subject is enrolled, but does not receive SRS
- The subject is enrolled as part of the safety run-in cohort and, for any logistical reason unrelated to the patient's clinical condition, does not receive all scheduled components of Cycle 1 treatment (i.e., a subject is enrolled on safety run-in cohort but does not receive all of the following: 3 fractions of radiation, C1D1 dose of INCMGA00012, C1D1 dose of INCAGN01876, and C1D15 dose of INCAGN01876). Examples of such logistical reasons include: the current lot of investigational product on site (INCMGA00012 or INCAGN01876) tests out of specification, the radiation machine breaks down in the midst of the subject's radiation, a spike in COVID-19 infections results in temporary suspension of clinical research at the study site, etc).

- The subject receives study drugs (+/- SRS), but becomes pregnant (and therefore is taken off study per study drug discontinuation criteria [Section 5.7](#)) before the first response evaluation (MRI) occurs
- The subject receives study drugs (+/- SRS), but consent is withdrawn by the subject before the first response evaluation (MRI) occurs
- The subject receives study drugs (+/- SRS), but is subsequently found not to have met eligibility criteria, AND the Medical Director, in collaboration with the investigator, determined that the subject should be withdrawn from the study, AND the first response evaluation (MRI) has not yet taken place
- The subject receives study drugs (+/- SRS), but is then noncompliant with study procedures in the investigator's opinion, AND the sponsor has been consulted and has determined that the subject should be withdrawn from the study, AND the first response evaluation (MRI) has not yet taken place

As long as the subject has not withdrawn his/her consent, the non-treated (replaced) subject is followed for safety follow-up per [Table 10](#) (see [Section 6](#)) and all safety-related data collected for the subject is included in analysis of the study's secondary safety/tolerability endpoints. However, the subject is not included in the primary endpoint efficacy analysis or in analysis of secondary efficacy endpoints (see [Section 8, Statistical Plan](#)). In addition, if the replaced subject was enrolled during the safety run-in phase, that subject will not be counted for purposes of determining whether the pre-specified safety criteria (see [Section 3.1; General Design](#)) have been met during the safety run-in phase to allow for successful completion of the safety run-in phase.

Subject replacement occurs up to and no more than 7 times for Cohort A [i.e., up to 23 subjects can be enrolled to obtain 16 subjects who receive both of the study drugs at the same dose and schedule AND SRS and are therefore evaluable for the primary endpoint].

Cohort B: Any subject who is enrolled onto Cohort B of the study but meets one of the following criteria is replaced by enrollment of a new subject onto Cohort B:

- The subject is enrolled, but does not receive either of the systemic agents (INCMGA00012, INCAGN01876)
- The subject is enrolled, but does not receive SRS (surgical subarm #1 only)
- The subject is enrolled, but does not undergo surgery

As long as the subject has not withdrawn his/her consent, the non-treated (replaced) subject is followed for safety follow-up per [Table 10](#) (see [Section 6](#)) and all safety-related data collected for the subject is included in analysis of secondary study endpoints.

Subject replacement occurs up to and no more than 10 times for Cohort B [i.e., up to 26 subjects can be enrolled to obtain 16 subjects who receive neoadjuvant therapy AND undergo surgery, with 8 patients assigned to each of the 2 sub-arms]. Subjects who need to be replaced in Cohort B, will be replaced by a subject enrolled onto the same sub-arm that the replaced subject was previously on.

Replaced subjects will be followed for safety only. These subjects will not be included in efficacy endpoint analyses, and they will not have tumor tissue available for correlative endpoint analyses.

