If at any point during the safety run-in a stopping rule is met and the dose/schedule of investigational agents is changed, and the safety-run in phase is then successfully completed at the new dose/schedule, 16 additional subjects will be enrolled in Cohort A at the new dose/schedule to achieve the desired sample size of 16 subjects that are evaluable for the study’s primary endpoint. Thus, the total sample size for Cohort A could potentially be more than 16 subjects (e.g., 6 subjects are enrolled in the initial safety run-in and 3 of them experience a toxicity requiring study drug discontinuation; an additional 6 subjects are then enrolled at the new dose/schedule that has been decided upon, and this time the safety run-in is completed successfully with only 1 subject discontinuing study drug due to toxicity; we would then enroll 10 additional subjects at the current dose/schedule of study drugs to achieve 16 evaluable subjects treated at the final dose/schedule; the total sample size for cohort A in this example would be 22 subjects).

Cohort B will not start enrollment until the safety run-in phase has been successfully completed.

Details of treatment administered in each cohort are provided below in [Section 3.1.2, Study Intervention Phase](#).

[figure not shown]

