3.5 Total Number of Subjects and Sites

This is a single center study and subjects are only recruited from the University of Pennsylvania. Recruitment for Cohort A ends when (1) the safety run-in phase has been successfully completed AND (2) 16 subjects in Cohort A have received at least one dose of each study drug at the same dose/schedule as determined by the safety run-in phase. Greater than 16 total subjects may be enrolled on Cohort A if the stopping rule for toxicity is met during the safety run-in phase (see [Section 3.1 General Design](#)). The maximum possible sample size for Cohort A is 22 subjects who are evaluable for the study's primary efficacy endpoint, which would occur if enrollment of 12 subjects (which is the maximum allowed for the safety run-in phase) is necessary to successfully complete the safety run-in phase and an additional 10 subjects are enrolled at the same finalized dose/schedule of study drugs that was given to the last 6 subjects enrolled on the safety run-on phase.

Recruitment for Cohort B ends with 16 subjects have received study drug(s) AND surgery.

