6.2. Subject Withdrawal from the Study

Subjects may withdraw consent for the study at any time for any reason without impact to their care. In addition, a subject may be withdrawn by the investigator or the sponsor if enrollment in the study is inappropriate, lack of adherence to the intervention or study procedures or visit schedules, the study plan is violated, or for administrative and/or other safety reasons. It is documented whether or not each subject completes the clinical study. If the subject actively withdraws consent for collection of follow-up data (i.e., subsequent anticancer treatments, safety follow-up, and survival), then no additional data collection occurs; however, all subjects are informed of the option to discontinue treatment and/or study assessments but allow collection of information in the follow-up period of the study. In the event that the latter occurs, the end-of-treatment (EOT) visit should be conducted (see **Table 8** and **Table 9** for EOT visit procedures). Thereafter, the subject will return for follow-up visits for safety and disease/survival status, with procedures as outlined above in **Table 10**.

If a subject withdraws from the study and has not yet received a dose of study drug, that subject is replaced according to the procedure outlined in **Section 3.2; Replacement of Subjects**.

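### The Cohort A recruitment stop in 3.5 does not match the evaluable set in 8.1 and 3.2, so recruitment can end with fewer than the 16 evaluable subjects that 80% power needs

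*Combined protocol and SAP*

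**What the plan says.** All sections are in the combined protocol and SAP and concern Cohort A.

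**Text that excludes replaced subjects**
- Section 3.2, on a replaced subject: "the subject is not included in the primary endpoint efficacy analysis or in analysis of secondary efficacy endpoints".
- Section 8.1 makes evaluability a conjunction: not replaced, and treated with SRS and at least one dose of both drugs.

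**Replaced subjects can be treated subjects**
- Four grounds in 3.2 start from a subject who has received study drug, with or without SRS, and then leaves before the first response MRI: pregnancy, ineligibility, noncompliance, and the case in which the subject was treated "but consent is withdrawn by the subject before the first response evaluation (MRI) occurs".
- A run-in subject is also replaced who, for logistical reasons, "does not receive all scheduled components of Cycle 1 treatment". That can be someone with both day-1 doses and one or two SRS fractions.
- Section 3.2 nevertheless labels the whole group untreated: "the non-treated (replaced) subject is followed for safety follow-up".

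**Text that counts by treatment received**
- The bracket in 3.2 refers to subjects "who receive both of the study drugs at the same dose and schedule AND SRS and are therefore evaluable for the primary endpoint".
- Limb (b) of 8.2.1 asks for at least one dose of both drugs and at least one SRS fraction. Limb (a) asks that the subject be one of the 16 at the final dose and schedule. Neither mentions replacement.
- Section 3.5 ends recruitment when the run-in is complete and "16 subjects in Cohort A have received at least one dose of each study drug at the same dose/schedule".

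**The target**
- Section 8.2.1 requires 16 evaluable subjects for 80% power. The worked example in 3.1 likewise enrols "to achieve 16 evaluable subjects treated at the final dose/schedule". Section 3.2 orders a new enrolment for each replaced subject, up to 7 times.

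**The concern.** The event that closes recruitment is not the event that makes a subject analysable. A subject given both drugs counts towards the 16 in 3.5 even if SRS is never delivered, or if the subject is later replaced. Section 8.1 then removes that subject from the primary analysis. No text says whether the stop in 3.5 or the replacement order in 3.2 prevails. If recruitment has closed, the analysis has fewer than 16 subjects and the stated power is lost.

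A second issue comes from the exclusion rule itself and would remain if every section agreed. Subjects who were treated but left before any response MRI disappear from the denominator. They have no observed response, so removing them can only raise the observed ORR compared with counting them as non-responders. Consent withdrawal and judged noncompliance are the grounds most plausibly related to outcome.

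**Working it through.** **Inputs.** Section 8.2.1 gives null rate 5%, alternative 25%, one-sided alpha 0.05, an exact single-stage design and 16 evaluable subjects for 80% power. Section 3.2 gives the cap of 7 replacements. No response cutoff is stated, so it is derived here.

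**Formula.** P(X ≥ r | n, p) = 1 − Σ C(n, j) p^j (1 − p)^(n − j), summed over j = 0 to r − 1.

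**Step 1: reproduce the plan's figure (n = 16).**
- P(X ≥ 2 | 16, 0.05) = 0.189, too large.
- P(X ≥ 3 | 16, 0.05) = 1 − (0.4401 + 0.3706 + 0.1463) = 0.043.
- P(X ≥ 3 | 16, 0.25) = 1 − (0.0100 + 0.0535 + 0.1336) = 0.803.

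The cutoff is therefore 3 responders and the stated 80% reproduces. A search over n shows that 16 is the smallest size reaching 80%, so there is no slack.

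**Step 2: shortfall if 3.5 is applied as written.** Suppose recruitment stops at 16 dosed subjects, and 1, 2 or 3 of them are not evaluable under 8.1.

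| Analysed n | P(X ≥ 2), 5% | P(X ≥ 3), 5% | Power, P(X ≥ 3), 25% |
|---|---|---|---|
| 16 | 0.189 | 0.043 | 0.803 |
| 15 | 0.171 | 0.036 | 0.764 |
| 14 | 0.153 | 0.030 | 0.719 |
| 13 | 0.135 | 0.025 | 0.667 |

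A cutoff of 2 is never valid, so it stays at 3 and the whole loss falls on power.

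**Step 3: no shortfall if 3.2 is carried through.** With each replaced subject succeeded by a new one, up to 16 + 7 = 23 enrolled, 16 non-replaced subjects are reached and Step 1 applies unchanged. Fewer than 16 then arises only if more than 7 replacements are needed.

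**Step 4: effect of dropping treated subjects.** Assume that k treated subjects are dropped and replaced, that all k are non-responders, and that 5% is the true rate among all 16 + k treated. The documents give no expected k. Two ways of modelling this:
- Model A raises the rate among the 16 retained to 0.05 × (16 + k)/16 = 0.0531, 0.0563 or 0.0594 for k = 1, 2 or 3. P(X ≥ 3 | 16) is then 0.04995, 0.0575 or 0.0656.
- Model B places all responders among the 16 retained. P(X ≥ 3 | 16 + k, 0.05) is 0.0503, 0.0581 or 0.0666.

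The design value is 0.043. If leaving is unrelated to response, the retained rate is still 5% and alpha stays at 0.043.

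**Step 5: an all-treated denominator.** Three responders give p = 0.0429 out of 16 and p = 0.0503 out of 17. At n = 17 the lowest valid cutoff is 4, with power 0.647. A cutoff of 3 therefore cannot be carried over to a larger set.

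**The case against.** The strongest reply is that the analysis set can be determined. Section 8.1 and the exclusion sentence in 3.2 agree. Limb (a) of 8.2.1 fits them, since replacement is how the 16 are reached, and limb (b) does not define evaluability by itself. Replacement in 3.2 is mandatory, and 3.1 and 8.2.1 both aim at 16 evaluable subjects. Most of this stands. A reader might infer that the plan has no usable primary set, or that fewer than 16 will be analysed. The documents support neither: the weight of the text favours the non-replaced set, and the shortfall depends on 3.5 being applied over 3.2 or on the cap being exceeded. What remains is that 3.5 as worded conflicts with both sections, and that 8.2.1 restates evaluability without the condition in 8.1.

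A reader might also infer from 3 of 16 against 3 of 17 that the choice between sections decides the primary result. That needs limb (b) read without limb (a); read together, they keep the denominator at 16.

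The type I error result likewise does not follow from the inconsistency. It follows from the exclusion rule under assumed outcome-related leaving. Pregnancy, ineligibility and logistics have no evident link to response. Once both drugs and SRS have been given, death, deterioration, progression and toxicity are not replacement grounds.

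Section 6.2 ("If a subject withdraws from the study and has not yet received a dose of study drug, that subject is replaced") might be read as limiting replacement after withdrawal to undosed subjects. It does not say so, and it refers back to 3.2.

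**Conclusion.** The mismatch between 3.5 and the evaluable set in 8.1 and 3.2 is real and should be fixed. If 3.5 is followed literally and 1, 2 or 3 of the 16 are not evaluable, power is 0.764, 0.719 or 0.667 instead of 0.803. If 3.2 is followed within its cap, power is as planned. The sample size calculation itself is correct.

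The exclusion of treated subjects is a separate and smaller matter. Alpha of about 0.050, 0.058 or 0.066-0.067 for one, two or three dropped subjects rests on an assumed k, on every dropped subject being a non-responder, and on 5% holding among all treated.

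It is tempting to conclude that the primary set should become the first 16 treated, with unassessed subjects counted as non-responders. The documents do not require this. It would reverse a stated rule, and if 25% holds only among assessed subjects it gives the same power of 0.764, 0.719 or 0.667 with 1, 2 or 3 unassessed. An all-treated count is better placed as a sensitivity analysis.

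**What to change.** 1. In 3.5, end Cohort A recruitment when 16 subjects are evaluable as in 8.1, subject to the cap of 7 in 3.2. Evaluable means not replaced, at least one dose of both drugs, at least one SRS fraction, and the final dose and schedule.
2. Use that definition word for word in 3.2, 8.1 and 8.2.1. At present 8.1 says only that SRS was received and omits the dose and schedule condition, while 8.2.1 omits replacement. Stop describing replaced subjects as untreated where they were treated.
3. Prespecify a sensitivity analysis of ORR in all Cohort A subjects at the final dose and schedule who had both drugs and at least one SRS fraction, replaced or not. Count anyone without a confirmed response as a non-responder, and use the exact test for the actual n rather than carrying over the cutoff of 3.

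The cost is wording in four sections and one additional analysis. No patients are needed beyond the replacements that 3.2 already allows, and the run-in safety count is unchanged. The downside is that ORR in the sensitivity set may be slightly lower than in the primary set.

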3 INVESTIGATIONAL PLAN

3.1. General Design

This is a single-center, phase II, open label study evaluating the efficacy and safety of the combination of INCMGA00012, INCAGN01876 and SRS for patients with recurrent GBM.

The overall study population will be broken down into two cohorts: Cohort A (N=16) and Cohort B (N=16). Subjects for whom surgical resection is not clinically indicated at the time of study

screening will be enrolled into Cohort A (non-surgical cohort). Subjects for whom surgical resection is clinically indicated at the time of study screening will be enrolled into Cohort B (surgical cohort).

The first 6 subjects enrolled onto the study must be enrolled onto Cohort A and will be enrolled in two groups of 3 subjects (i.e., a “3+3” design) as part of a safety run-in period. After enrollment of the first 3 subjects, enrollment is put on hold until all of the first 3 subjects have completed the safety monitoring period (completion of SRS and one cycle of INCMGA00012 and INCAGN01876). If only 0-1 of the first 3 subjects experiences a criterion for study drug discontinuation, as defined in [Section 5.7, Study Drug Discontinuation Criteria](#), then the next 3 subjects will be enrolled. If 2 of the first 3 subjects experience a criterion for study drug discontinuation, the study will be paused for reconsideration of the dosing and schedule of investigational agents.

Of the first 6 subjects enrolled during the safety run-in, if 3 or greater subjects experience a criterion for study drug discontinuation, then the study will be paused for reconsideration of the dosing and schedule of investigational agents. If only 0-2 of the first 6 subjects enrolled during the safety run-in experience a criterion for study drug discontinuation, then enrollment to both cohorts A and B will commence uninterrupted.

If at any point during the safety run-in a stopping rule is met and the dose/schedule of investigational agents is changed, the safety run-in will start over again with another 6 patients. If Cohort A has reached enrollment of 12 subjects and the criteria to move beyond the safety run-in phase has still not yet been met (i.e., at least 6 patients have been treated at the same dose/schedule and only 2 or fewer have experienced a criterion for study drug discontinuation), the trial (including Cohort B) will be terminated due to intolerability of the study regimen.

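### Sections 3.1 and 3.2 do not settle whether a dosed run-in subject with early toxicity, who then misses the second drug or SRS, counts in the safety run-in decision

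*Combined protocol and SAP*

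**What the plan says.** **Pause and pass rules (3.1 General Design).** The first trigger reads "If 2 of the first 3 subjects experience a criterion for study drug discontinuation, the study will be paused". The second begins "Of the first 6 subjects enrolled during the safety run-in, if 3 or greater subjects experience a criterion for study drug discontinuation". The run-in is passed when "at least 6 patients have been treated at the same dose/schedule and only 2 or fewer have experienced a criterion for study drug discontinuation". If this has not been reached by a fixed enrolment, the trial ends: "If Cohort A has reached enrollment of 12 subjects".

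**Replacement (3.2, Cohort A).** The first reason is "The subject is enrolled, but does not receive BOTH systemic agents". The second is not receiving SRS. Neither limits the cause. The third applies only to the run-in. It covers an incomplete Cycle 1 (three radiation fractions, the day 1 dose of each drug, the day 15 dose of INCAGN01876), and only for logistical causes that have nothing to do with the patient's condition.

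**Effect of replacement (3.2).** For a subject replaced during the run-in, "that subject will not be counted for purposes of determining whether the pre-specified safety criteria" are met. The sentence refers to 3.1 for these criteria and ties the exclusion to whether they "have been met during the safety run-in phase to allow for successful completion of the safety run-in phase". The subject's safety data stay in the secondary safety analysis.

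**Evaluability.** Toward its target number, 3.2 counts only "subjects who receive both of the study drugs at the same dose and schedule AND SRS and are therefore evaluable for the primary endpoint". Sections 8.1 and 8.2.1 set the same condition.

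**The concern.** The run-in is the trial's only formal toxicity gate, and it opens both cohorts. 3.1 counts events among subjects enrolled. The first two replacement reasons in 3.2, followed as written, take a subject out of that count even when toxicity is why the second drug or SRS was missed. The same data can then pause the study under one section and let it continue under the other, and the site would have to choose a reading after seeing the toxicity.

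The situation can arise. INCMGA00012 is infused before INCAGN01876 on the same day (5.5.1), and SRS starts 3 to 7 days after the first doses (Table 8 footnote). Some 5.7 criteria can be met within that week: a grade 4 immune-related event, one of the listed grade 3 events, transverse myelitis, a grade 3 or higher infusion reaction, or a drug-related event judged to compromise study procedures. A subject who permanently stops the study drugs goes to follow-up (3.1.3).

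**Working it through.** **1. The plan's own figure.** Cohort A: N=16, response rate 5% against 25%, one-sided 0.05 (8.2.1). With success at 3 or more of 16, the exact binomial gives alpha 0.0429 and power 0.8029; N=15 gives 0.7639. The stated 80% is reproduced. The run-in count does not enter it, so N and power are unaffected. The plan gives no operating characteristics for the run-in.

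**2. Cases that need no rate.**
- Two of the first 3 meet a toxicity criterion, one of them before SRS and then not irradiated. 3.1: 2 of 3, pause. Literal 3.2: 1 counted, a replacement is enrolled, no pause at that point.
- Three of the first 6 meet a criterion, one of them in this way. 3.1: 3 of 6, pause. Literal 3.2, after an event-free replacement: 6 treated, 2 counted, pass.

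**3. Inputs for the size.**
- Event rate p = 4/56 = 7.1%: dose-limiting toxicities on INCAGN01876 300 mg plus nivolumab (1.3.2.2). There was no SRS, and these toxicities are not the same as 5.7 criteria. The exact 95% interval is 2.0% to 17.3%; the upper limit is used as a second value.
- Rate e of events that literal 3.2 would drop: not in the documents. Assumed 0.5% to 2.5%. The upper value is close to 5/199, all infusion reactions to INCMGA00012 (5.5.1). That covers any grade and any infusion, so it overstates early severe reactions, but it leaves out other early events.
- 3.1 does not mention 3 of 3; it is treated as a pause.

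**4. Formulas.** With X1 and X2 each Bin(3, q):

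Pass(q) = P(X1=0)·P(X2≤2) + P(X1=1)·P(X2≤1)

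If every event counts, q = p. If early events are dropped and those subjects replaced, q = (p − e)/(1 − e). The replacement cap and the 12-subject limit are ignored.

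- p = 0.0714: 0.8007×0.9996 + 0.1848×0.9854 = 0.9824
- p = 0.1729: 0.5658×0.9948 + 0.3548×0.9207 = 0.8896

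| p | e | q | Pass, all counted | Pass, early dropped | Rise (points) |
|---|---|---|---|---|---|
| 0.0714 | 0.005 | 0.0668 | 0.9824 | 0.9848 | 0.2 |
| 0.0714 | 0.025 | 0.0476 | 0.9824 | 0.9925 | 1.0 |
| 0.1729 | 0.005 | 0.1687 | 0.8896 | 0.8949 | 0.5 |
| 0.1729 | 0.025 | 0.1517 | 0.8896 | 0.9155 | 2.6 |

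**5. Given that one such case occurs (other subjects at 4/56).**
- Among the first three, counted: (1 − p)²·P(Bin(3,p)≤1) = 0.8622×0.9854 = 0.8497. Dropped: 0.9824. Difference 13.3 points.
- Among subjects 4 to 6, counted: P(X1=0)·P(Bin(2,p)≤1) + P(X1=1)·(1 − p)² = 0.8007×0.9949 + 0.1848×0.8622 = 0.9559. Dropped: 0.9824. Difference 2.7 points.
- Chance of at least one among six: 1 − 0.995⁶ = 3.0%; 1 − (1 − 5/199)⁶ = 14.2%.

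**The case against.** Several features of the text point towards counting the event. The third replacement reason is specific to the run-in and covers the same Cycle 1 components, so it may be thought to govern, and it excludes clinical causes. 3.2 calls the replaced subject non-treated. Its later reasons speak of subjects who received drug with or without SRS, whereas the first two speak only of being enrolled. The exclusion is tied to successful completion, so it might mean only that the subject cannot fill a place in a pass while the pause triggers still count the event. Section 3.5 closes Cohort A on doses of each drug, without an SRS condition.

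These points make it likely that toxicity-driven omissions were meant to count, but none of them overrides the first two reasons. The non-treated label follows a list that includes dosed subjects. The evaluability rule needs the second reason to reach subjects who were dosed but not irradiated. The pass criterion contains the event count itself, so leaving out the subject also leaves out the event.

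The objection on scope stands. No passage says SRS is withheld after a 5.7 event. The broad grade 2 criterion allows up to 12 weeks for improvement and cannot be met in the first week. After a reaction linked to one drug, the other may continue. Safety information is not lost: adverse events stay in the safety analysis, serious ones reach the Sponsor within 24 hours (9.3.2), and the sponsor may end the study on emerging data (3.4).

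**Conclusion.** The point holds as an unresolved conflict between 3.1 and 3.2 over one kind of subject, and it should be fixed. On average the effect is small: 0.2 to 1.0 points at 4/56 and 0.5 to 2.6 points at 17.3%, resting on an assumed 0.5% to 2.5% early-event rate and on a dose-limiting-toxicity rate from a regimen without SRS. It matters mainly when the case occurs among the first three subjects: 85.0% against 98.2%.

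Three stronger readings are not supported.
- A reader might infer that the plan intends to discard early toxicity. The logistical limit in the third replacement reason suggests the opposite.
- A reader might assume that up to half of all events are dropped. At 17.3% that means 0.5×17.3% = 8.6% of subjects with an event this early, more than three times the 2.5% upper assumption, which is itself generous for early severe infusion reactions.
- A reader might see the same conflict for pregnancy and consent withdrawal, which appear in both 5.7 and 3.2. There 3.2 expressly orders replacement, and neither is a toxicity.

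**What to change.** Reconcile 3.1 and 3.2 so that each run-in subject has one count:
- Give the exclusion from the run-in count the limit that the third replacement reason already carries, so that it applies only where the cause is unrelated to the subject's clinical condition.
- State that a dosed subject with a 5.7 toxicity event stays in the 3.1 event count even if replaced for the efficacy analysis.
- State whether replaced subjects count toward the 12-subject run-in limit. If they do, a restart after a full six (6 + 6 = 12) leaves no room for a single replacement.

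This takes a few sentences in 3.2 and a cross-reference in 3.1. The cost is that the run-in may pause slightly more often than under the literal reading, by the points shown in the table, and a pause followed by a change of dose or schedule restarts it. No dose, treatment rule or evaluable number changes, and whether SRS is given after a 5.7 event is left as it is.
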